13 ADVERSE EVENT REPORTING AND MEDICAL MONITOR.....	22
13.1 Reporting adverse events.....	22
13.2 Definition of SAE.....	23
14 SUB SITES:.....	24
15 MEDICAL MONITOR	24

15.1	Sub-sites	24
15.2	DSMB safety Review	25
15.3	Stopping Rules	25
15.4	Sub-sites	25
16	RESEARCH CONFLICT OF INTEREST	25
17	COST TO SUBJECTS.....	25
18	APPENDIX 1 - LENT/SOMA CRITERIA: LATE REACTIONS	26
19	APPENDIX 2 - TOXICITY TRACKING FORM	27
20	APPENDIX 3 – QUALITY OF LIFE QUESTIONNAIRES	28
20.1	Appendix 3.1 Quality of Life questionnaire used at baseline	28
21	APPENDIX - QUALITY OF LIFE QUESTIONNAIRE USED FOR FOLLOW-UP VISITS	35
22	APPENDIX - FORM FOR MISSING QUALITY OF LIFE INFORMATION	41
23	REFERENCES	42

DOCUMENT HISTORY

Document Name	Protocol version	Protocol Version Date
Amendment 8	Version 7.0	06DEC2024
Amendment 7	Version 6.0	07OCT2024
Amendment 6	Version 5.0	05JUL2023
Amendment 5	Version 4.0	21OCT2022
Amendment 4	Version 3.0	09JAN2021
Amendment 3	Version 2.2	13OCT2020
Amendment 2	Version 2.1	23MAR2020
Amendment 1	Version 2.0	18NOV2019
Initial	version 1.0	06NOV2019

Summary of changes for Protocol version 7.0 dated 06DEC2024

Section(s)	Changes	Rationale
Protocol Summary	Increasing the accrual ceiling from 420 to 430 subjects	Based on the number of patients that withdrew, the statistician recommends increasing the accrual ceiling from 420 to 430, to ensure to achieve the planned sample size of 400 patients

Summary of changes for Protocol version 6.0 dated 07OCT2024

Section(s)	Changes	Rationale
Protocol Summary, Objectives	Clarifying that, according with statistical consideration, the primary hypothesis and the primary endpoint of the study is the acute toxicity	Harmonization and consistency of the study protocol
Treatment plan, toxicities to be monitored and dosage modifications, study calendar	Clarifying that Breast cosmesis will be self-assessed by the patient using BCTOS questionnaires, before treatment (baseline), at the end of RT, at 1-month follow up visit and at 2-year follow up visit. The receipt of the survey will be recorded by the research nurses assigned to the study, but completion is not mandatory. Quality of life surveys will be sent to the patients' personal email address at the baseline, at the end of RT, at 1-month follow up visit and at 2-year follow up visit. Completed responses will be sent directly to our REDCAP database. The quality of life survey completion is optional.	Harmonization and consistency of the study protocol

Protocol Summary, Objectives, Study Calendar, Statistical and Data Management Considerations	Reporting the outcomes of late toxicity, breast cosmesis and local control at 2-3 years as well as at 5 years	To assess late toxicity, breast cosmesis and local control at 2-3 years, as well as at 5 years, because early results can provide valuable insights into the effectiveness and tolerability of treatments.
Patient Eligibility	Adding to inclusion criteria: women with previous contralateral breast cancer	A history of contralateral breast cancer does not compromise the radiotherapy treatment plan or the outcomes being assessed in this study.
Study Calendar	Removing KPS and Body weight	These data are redundant and not relevant for the study purpose
ECL	Adding to inclusion criteria: women with previous contralateral breast cancer	To reflect the change proposed in the section “Patient Eligibility”
No changes to the informed consent		

Summary of changes for Protocol version 5.0 dated 05JUL2023

Section(s)	Changes	Rationale
Cover page	Updating cover to reflect only the PI and the Co-PIs	To reduce multiple amendments that result due to change of personnel we will only have PI and the Co-PI information on the cover page.
No changes to the informed consent		

Summary of changes for Protocol version 4.0 dated 21OCT2022

Section(s)	Changes	Rationale
------------	---------	-----------

Adding personnel from Network sites	Adding personnel: NYP-Queens: [name], [name], [name], [name], [name], [name]. NYP-BMH: [name], [name] NYP-WCM – [name] and [name] (to IRB application. Note that [name] was already approved before. Removing [name], [name] and [name] from the study.	Adding and removing Personnel.
13.1 Reporting Adverse events	1. Clarifying that CTCAE version 5.0 will be used for this study. 2. Clarifying the DSMB will be reviewing Grade 3 and above events including SAEs. 3. Adding AE and SAE definitions.	Based on the DSMB memo issued on 24MAY2022.
Informed Consent changes		
Adding Key information section	Adding Key information section.	IRB requested changes.

Summary of changes for Protocol version 3.0 dated 09JAN2021.

Section(s)	Changes	Rationale
Adding Network sites	Adding NYP-BMH, NYP-Q as addition sites for patient enrollments	Adding sites.
Adding network sites	Adding NYP-BMH, NYP-Q as addition sites for patient enrollments	Adding sites

Summary of changes for Protocol version 2.2 dated 13OCT2020.

Section(s)	Changes	Rationale
Study Team	Adding [name] to the study team as key personnel. Removing [name] and [name] from the Personnel section	Personnel changes

Summary of changes: Version 2.1 Dated 23MAR2020

Sections 6.1.6, section 8.1 and section 9 have been modified to include the following statement:

“Quality of life surveys will be sent to the patients’ personal email address. Completed responses will be sent directly to our REDCAP database.”

Summary of Changes: Version 2.0 Dated 18NOV2019

1. Page 8 Hypothesis: ARM 2 boost dose was incorrect and has been changed to 4200cGY.
2. Page 6 schema had N0-1 and this has been changed to N0. This has been made consistent across the protocol.
3. Section 7.3 Treatment duration section has been revised to state that, the whole breast will be treated for five consecutive fractions for either three (Arm 1) or two (Arm 2) consecutive weeks.

[figure not shown]
Informed Consent changes:

1. The footer of the informed consent has been changed to indicate the correct version of the protocol.

No other changes have been made in the informed consent.

SCHEMA

These exams, tests or procedures are part of regular cancer care and may be done even if you do not join the study.

Protocol Summary

Full Title: Prospective Randomized study of Accelerated Radiation Therapy (PRART): a Non-Inferiority Trial to Compare Breast Cosmesis and Local Control after Concomitant Boost Breast Radiotherapy with Fifteen Fractions in Three Weeks (arm 1, standard) versus Ten Fractions in Two Weeks (arm 2, experimental)

Short Title: Randomized

Clinical Phase: Phase III

Principal Investigators: Drs. [name] and [name]

Sample Size: N= 400 (200 per Arm)

Accrual Ceiling: 430

Rate of subject accrual: Approx. 8 subjects per month or 100 patients per year

Study Population: S/p segmental mastectomy patients with Tis (DCIS), T1-T2, N0 breast cancers.

Accrual Period: 4 years

Study Design: Patients with Tis (DCIS), T1-T2, N0 breast cancers will be randomized to receive whole breast radiotherapy with a concomitant boost to the tumor bed over 15 fractions (Arm 1, standard) versus 10 fractions (Arm 2, experimental).

Study Duration: 10 years to report: 2-3 years and 5 years late toxicity, local control rate, and breast cosmesis.

Intervention Description: Radiotherapy: 4050cGy whole breast radiotherapy with a concomitant tumor bed boost to 4800 cGy to the tumor bed in 15 fractions (Arm 1) versus 3200cGy whole breast radiotherapy with a concomitant tumor bed boost to 4200 cGy in 10 fraction (Arm 2).

Hypothesis: A regimen of whole breast radiotherapy to 3200cGy with a concomitant tumor bed boost to 4200 cGy in 10 fractions (Arm 2) is not inferior to the current standard of whole breast radiotherapy of 4050 cGy with a concomitant tumor bed boost to 4800 cGy in 15 fractions (Arm 1), in terms of acute toxicity and long-term fibrosis, breast cosmesis and local control, at 2-3 years and at 5 years.

Primary Objectives: 1. To prospectively randomize patients to one of two hypo-fractionation regimens of concomitant boost breast radiotherapy as part of breast conservation therapy in patients with T1-2N0 breast cancers or Stage 0 (Tis) DCIS: 4050cGy whole breast radiotherapy with a concomitant tumor bed boost to 4800 cGy to the tumor bed in 15 fractions (Arm 1) versus 3200 cGy whole breast radiotherapy with a concomitant tumor bed boost to 4200 cGy in 10 fractions (Arm 2).

2. To test the primary hypothesis that the proportion of patients with grade ≥ 2 acute toxicity with 2 weeks regimen (10 fraction arm) would not be $> 5\%$ greater than the rate of 10% with a standard 3weeks regimen (15 fraction arm).

Endpoints:

Primary endpoint is the rate of acute toxicity. Expected acute toxicities include fatigue and skin reactions within the radiation field. Erythema, dry and wet desquamation of the skin will be recorded weekly, during RT treatment. The toxicities will be graded by the research nurses assigned to the study according to Common Terminology Criteria for Adverse Events, version 5.0.

Secondary endpoints are the evaluation at 2-3 years and 5 years of fibrosis, breast cosmesis and local control. The LENT/SOMA scoring system will be used in the reporting of late radiation morbidity, including fibrosis, at baseline (prior to treatment) and at each subsequent follow-up after completing radiotherapy, scored by the research nurses assigned to the study. Breast cosmesis will be assessed using the BCTOS patient self-reports before treatment (baseline), at the end of RT, at 1-month follow up visit and at 2-year follow up visit. Local control at 2-3 years and at 5 years will be extracted from the medical record, and can be derived from clinical reports from medical, surgical or radiation oncologists as well as from the primary care doctor who is following the patient.

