7.3 Treatment duration

The whole breast will be treated for five consecutive fractions for either three (Arm 1) or two (Arm 2) consecutive weeks.

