9 STUDY CALENDAR

All patients will be followed a month after the completion of treatment. Our routine follow up is once a year after completion of radiation therapy. **For the purpose of protocol significance (for assessment of fibrosis), we will require at least one follow up in the department visit after the**

second year. Acute and late effects will be recorded following the criteria described in Appendix 1. At each post treatment follow-up visit, a physical exam to detect clinical recurrence will be performed. Mammographic studies and/or MRI will be performed and reviewed on an annual basis.

The degree of fibrosis assessed by palpation will be measured as per Appendix 1, late effects at 2-3 years and at 5 years. Local control at 2-3 years and at 5 years will be extracted from the medical record, and can be derived from clinical reports from medical, surgical or radiation oncologists as well as from the primary care doctor who is following the patient.

Table 4: Study Calendar

Study	Pre Entry	Weekly[‡]	Post Treatment Follow-up visits
Mammogram	X		X**
Lumpectomy pathology report	X		
Medical History	X		X*
BCTOS and quality of life surveys[⊕]	X		X
Physical exam	X	X	X*
Consent Form	X		
Randomization	X		
Treatment simulation	X		
Weekly CBCT prior to RT treatment		X	
Port films/ each RT dose after the first one		X	
Skin Assessment	X	X	X*

[‡] - performed weekly during the weeks of radiation therapy.

* Our routine follow up is once a year after completion of radiation therapy. For the purpose of protocol significance (for assessment of fibrosis), we will require at least one follow up visit after the second year.

** Standard annual mammogram (or MRI) for both breasts will be accepted as follow up data.

⊕ Quality of life surveys will be sent to the patients' personal email address. Completed responses will be sent directly to our REDCAP database. The quality of life survey completion is optional. The receipt of the BCTOS survey will be recorded by the research nurses assigned to the study, but completion is not mandatory. The BCTOS and quality of life questionnaires will administer before treatment (baseline), at the end of RT, at 1-month follow up visit and at 2-year follow up visit.

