17 COST TO SUBJECTS

Each subject or their insurance company will be charged and held responsible for the costs of care provided as part of this study. Radiotherapy is a standard treatment for breast cancer and will be billed to subjects and their insurance companies.

There will be no monetary compensation for participating in this study.

18 APPENDIX 1 - LENT/SOMA Criteria: Late Reactions

Table 1. RTOG/EORTC and LENT/SOMA classification of late effects				
RTOG/EORTC	Grade 1	Grade 2	Grade 3	Grade 4
Skin	Slight atrophy, pigmentation change, some hair loss	Patchy atrophy, moderate telangiectasia, total hair loss	Marked atrophy, gross telangiectasia	Ulceration
Subcutaneous tissue	Slight induration (fibrosis), and loss of subcutaneous fat	Moderate fibrosis, but asymptomatic; slight field contracture, $\leq 10\%$ linear reduction	Severe induration and loss of subcutaneous tissue, field contracture, $\geq 10\%$ linear reduction	Necrosis
LENT/SOMA				
Breast				
Subjective				
Pain	Occasional and minimal	Intermittent and tolerable	Persistent and intense	Refractory and excruciating
Objective				
Telangiectasia	$< 1 \text{ cm}^2$	$1-4 \text{ cm}^2$	$> 4 \text{ cm}^2$	
Fibrosis	Barely palpable, increased density	Definite increased intensity and firmness	Very marked density, retraction, and fixation	
Edema	Asymptomatic	Symptomatic	Secondary dysfunction	
Retraction, atrophy	$10-25\%$	$> 25-40\%$	$> 40-75\%$	
Ulcer	Epidermal only, $< 1 \text{ cm}^2$	Dermal only, $> 1 \text{ cm}^2$	Subcutaneous	Whole breast Bone exposed, necrosis
Lymphedema, arm circumference	$2-4\text{-cm}$ increase	$> 4-6\text{-cm}$ increase	$> 6\text{-cm}$ increase	Useless arm
Skin				
Pigmentation change	Transitory, slight	Permanent, marked	—	—
Abbreviations: RTOG = Radiation Therapy Oncology Group; EORTC = European Organization for Research and Treatment of Cancer; LENT = Late Effects Normal Tissue Task Force; SOMA = subjective, objective, management, and analytic.				

Please, refer to the following link for the Common Terminology Criteria for Adverse Events, version 5.0

https://ctep.cancer.gov/protocoldevelopment/electronic_applications/docs/ctcae_v5_quick_reference_5x7.pdf

19 Appendix 2 - Toxicity Tracking Form

PHYSICIAN'S PROGRESS NOTE

Fraction: ☐ 1-5 ☐ 6-10 ☐ 11-15 ☐ 1 mo F/U ☐ 3 mo F/U

The following critical elements of the patient's weekly exam have been covered:

- ☐ *Chart & Dosimetry, Treatment set up & positioning review*
☐ *Port Film or image review*

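### The primary endpoint states no common assessment window; the only collection rule in its own text gives three weekly looks in Arm 1 and two in Arm 2

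*Combined protocol and SAP*

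**What the plan says.** **Endpoint text.** The Protocol Summary, under Endpoints, says "Primary endpoint is the rate of acute toxicity". The only timing given there is "Erythema, dry and wet desquamation of the skin will be recorded weekly, during RT treatment", and Section 8 repeats it. The footnote to the weekly column of Table 4 (Section 9) reads "performed weekly during the weeks of radiation therapy". Section 7.3 sets the length of that period: "The whole breast will be treated for five consecutive fractions for either three (Arm 1) or two (Arm 2) consecutive weeks".

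**Post-treatment collection.** Section 9 says "All patients will be followed a month after the completion of treatment" and "Acute and late effects will be recorded following the criteria described in Appendix 1". Table 4 also marks skin assessment in the post-treatment column, with a footnote about annual follow-up and a visit after year 2. Section 10 refers the reporting of acute and late toxicity to the calendar. The tracking form in Section 19 (Appendix 2) carries the boxes "Fraction: ☐ 1-5 ☐ 6-10 ☐ 11-15 ☐ 1 mo F/U ☐ 3 mo F/U". Sections 13 and 13.1.1 have adverse events recorded throughout participation, Section 13.1.3 asks for every change of grade within an episode, and Section 14 has sub-sites enter events at each follow-up visit.

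**Test.** Section 11 tests the proportion with grade ≥2 acute toxicity (control rate 10%, margin 5 percentage points, one-sided 0.025, 400 patients). It names no window and no list of qualifying visits.

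**The concern.** Read literally, the endpoint text ties the observation period to the treatment being compared: the arm treated for longer is watched for longer and graded once more. In a non-inferiority comparison, missed events in the experimental arm make it look safer than it is. If Arm 2's reactions reach grade ≥2 after its second week more often than Arm 1's do after its third, the recorded rates are not the same quantity, and the test can accept a regimen whose true excess is at the margin. An undefined window also leaves the choice of qualifying records open until data are in hand.

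**Working it through.** **1. Looks per arm.** One assessment per treatment week gives 3 in Arm 1 and 2 in Arm 2. On the Appendix 2 form, Arm 2 can never use the box for fractions 11-15.

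**2. Method and the plan's own figure.** The plan does not name its test statistic, so I assume the unpooled normal approximation with 200 per arm:

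P(declare non-inferiority) = Φ( [0.05 − (p2 − p1)] / √{[p1(1−p1) + p2(1−p2)]/200} − 1.96 ),

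where p1 and p2 are the rates as recorded in Arms 1 and 2. With 10% in both arms, the result is Φ(0.05/0.03 − 1.96) = 38.5%, not the stated 79%. That mismatch is a separate matter: the false-positive calculation below does not depend on the power figure.

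**3. False non-inferiority if only on-treatment records count.** Let Arm 1's recorded rate be 10% and Arm 2's true rate 15%, exactly at the margin. Let c be the share of Arm 2 events recorded relative to Arm 1, so p2 = 0.15c. The values of c are assumptions.

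| c | p2 | 0.05 − (p2 − p1) | SE | P(non-inferiority) |
|---|---|---|---|---|
| 1.0 | 0.150 | 0 | 0.0330 | 2.5% |
| 0.9 | 0.135 | 0.015 | 0.0322 | 6.8% |
| 0.8 | 0.120 | 0.030 | 0.0313 | 15.8% |
| 0.7 | 0.105 | 0.045 | 0.0303 | 31.7% |
| 0.67 | 0.1005 | 0.0495 | 0.0300 | 37.8% |

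Simulating the three planned looks with the Section 11 boundaries gives 2.8%, 7.1%, 16.5%, 32.5% and 38.3%.

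**4. Only unequal capture matters.** With the final boundary of 1.98, full capture gives 2.4%. Capture of 95% in both arms (9.5% against 14.25%) gives 2.9%.

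**5. A constant weekly risk, as a second illustration.**
- True 10% over three weeks: the weekly risk is 1 − 0.90^(1/3) = 3.45%. Two weeks record 1 − (1 − 0.0345)² = 6.8%, an artificial advantage of 3.2 points. The chance of declaring non-inferiority goes from 38.5% to 84%.
- True 15% over three weeks: the weekly risk is 1 − 0.85^(1/3) = 5.27%. Two weeks record 10.3%, and non-inferiority is declared 35% of the time instead of 2.5%.

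**6. If the 1-month record counts.** Taking a month as 30 days, that visit falls near day 14 + 30 = 44 from the start of RT in Arm 2 and day 21 + 30 = 51 in Arm 1. Reactions still present then are captured in both arms. Arm 2 still has no assessment in week 3, when Arm 1 is examined, and the Appendix 2 form does not ask for the worst grade since the previous visit. The documents give no figure from which to size this remainder.

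**The case against.** A reader might infer that toxicity is recorded only while RT is running, that any reaction after the last fraction is lost, and that the comparison is therefore biased. The documents do not support this. The endpoint sentence sets an on-treatment frequency and does not say that collection ends there. Section 9 provides a 1-month visit for everyone and says acute effects are recorded. Section 10 ties acute toxicity to the calendar, the form has 1- and 3-month boxes, and Sections 13 and 14 continue adverse event recording into follow-up. Nor is Arm 2 simply unobserved for a week longer: the 1-month visit is timed from the end of treatment, so the gap after the last fraction is the same in both arms. The difference appears only when time runs from the start of RT. The larger percentages above also require that follow-up records be ignored and that Arm 2 lose about a third of its events relative to Arm 1.

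All of that stands and makes the bias conditional. It does not settle the definition:
- None of these provisions is tied to the grade ≥2 rate tested in Section 11.
- The post-treatment skin assessment in Table 4 is footnoted to annual follow-up, not to the 1-month visit.
- The form's 3-month box matches no visit in the calendar.
- The endpoint is graded by research nurses, whereas Section 13.1.3 assigns adverse event evaluation to a physician. The plan does not say these are one data source.

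**Conclusion.** The point holds as a gap in the endpoint definition with a possible bias toward non-inferiority. The protocol does not fix the window, its starting point, or the qualifying records for its primary rate, and the only rule in the endpoint text depends on the assigned arm. If on-treatment records alone are used, a relative loss of one tenth of Arm 2's events raises false non-inferiority from about 2.5% to about 7%; a loss of one fifth raises it to about 16%, and of one third to about 38%. These figures assume a recorded 10% in Arm 1, a true 15% in Arm 2, 200 per arm and the assumed capture values. If the 1-month record counts, the bias is smaller but the week-3 gap in Arm 2 remains. A reader should not conclude that the trial's result is biased: without onset timing, and without knowing which records will be used, the documents do not show that.

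**What to change.** Before the final analysis, and without looking at results by arm, define the primary endpoint as the worst CTCAE v5.0 grade from the first fraction to a fixed day after the **start** of RT. The day should be the same in both arms and late enough to include both 1-month visits. Day 60 is one example: it leaves about 16 days of slack for the Arm 2 visit (60 − 44) and 9 for Arm 1 (60 − 51). The quality-of-life forms already use a day 45 to 60 time point counted from the start of RT.

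Use the weekly visits plus the scheduled 1-month visit, recording there both the current grade and the worst grade since the last assessment. For patients already treated, use the existing 1-month records. Report the on-treatment-only rate as a sensitivity analysis. Either add the 3-month visit to the calendar or state that the 3-month box does not feed the primary endpoint.

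The cost is endpoint wording, one case report form field and abstraction of existing records. The drawbacks are reliance on recall for grades between visits and some missing 1-month visits. The number of on-treatment looks still differs (3 against 2), so the change reduces the imbalance without removing it entirely.
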